3.0 Investigational Plan / Schema

This is a single site Phase 2 interventional pilot study of euthyroid hypothyroxinemia in patients diagnosed with metastatic breast carcinoma. The study will enroll approximately 30 participants. It is anticipated that recruitment will take up to four (4) years. End of the study is the date of the last visit or last scheduled procedure for the last patient. An Intent-to Treat (ITT) population with a priori planned subgroup analysis will be used for analysis purposes.

Study Design: All enrolled participants will undergo baseline screening lab work (TSH, FreeT3, FreeT4, CBC, CMP), EKG and physical examination. Once it is determined that they meet eligibility criteria they will have their L-thyroxine (T4) discontinued and Triiodothyronine (T3) initiated. The Triiodothyronine (T3) will be titrated by the investigator to

maintain levels of free T4 < 50% normal range. Treatment duration will be 9 months. Disease status will be assessed at 3, 6, 9, and 12 months.

Eligibility Criteria

- Age greater than or equal to 18
- Male or female with diagnosis of metastatic breast carcinoma and documented history of hypothyroidism .
- TSH level within normal range at baseline
- Life expectancy estimated > 3 months
- Ability and willingness to provide informed consent

Exclusion Criteria

- Life expectancy estimated to be less than 3 months
- Is currently pregnant or intends to become pregnant during the duration of the study
- Active angina, NYHA advanced [Class III/IV] CHF, or uncontrolled cardiac arrhythmia within 6 months of enrollment
- History of thyrotoxicosis or adrenal insufficiency unless previously treated > 5 years ago and resolved without active replacement hormonal therapy as per Principal Investigator discretion.
- Hypersensitivity to any active or extraneous constituents in Cytomel/liothyronine sodium

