4.0 Study Procedures

It is anticipated that 20% of the patients with metastatic breast cancer will qualify for participation in this study. Patients who screen fail after meeting initial eligibility will be asked to allow record follow-up so the data can be used for the initial endpoint of prevalence. Rescreening will not be permitted.

Following consent and confirmation of eligibility participants will have their L-thyroxine (T4) discontinued and Triiodothyronine (T3)/liothyronine sodium initiated at 3: 1 mcg respectively. Study will allow use of Triiodothyronine (cytomel/liothyronine) and all available generic liothyronine sodium compounds. Triiodothyronine dosing will be rounded up to the closest commercial dose available. For patients on L-thyroxine there will be a washout period of four (4) days between discontinuation and the initiation of triiodothyroinine. Day 0 will be the day of enrollment. Day 1, or day 5 (if washout required) will be the day of the first dose of Triiodothyronine treatment. Triiodothyronine tablets are administered orally as a once a day dosing, or split dosing at the Investigators discretion. Usual maintenance dose is 25 to 75mcg daily. It will be recommended that the drug be taken at the same time each day, but this is not mandatory.

Drug titration will be in accordance with thyroid function testing to maintain levels of free T4 at <50% normal range. The treatment period will continue for 9 months (270 days). In the event of loco/regional recurrence or progression there is no need to discontinue study treatment because this is not one of the endpoints.

During the treatment period participants will have lab testing every 4 weeks for the first 12 weeks and then every 12 weeks until study drug is discontinued. Participants will be scheduled for a clinic visit every 12 weeks. Compliance with Triiodothyronine (T3) and adverse events will be assessed at each clinic visit. Disease state will be assessed at 3, 6, 9, and 12 months via clinical examination, laboratory results and radiographic findings performed as part of routine care. Participants will also be asked to complete a Quality of Life survey (FACT-B) at each clinic visit.

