Unscheduled visits and management for metastatic breast cancer are at the discretion of the investigator. Unscheduled visits may include physical examinations, vital signs, ECOG performance status, concomitant medication, adverse event collection, disease symptoms assessment, laboratory testing, Triiodothyronine (T3) dose adjustments, or to resumed dosing, if previously interrupted.

Discontinuation of Study Treatment: At the end of the treatment period, the investigator will have the discretion to resume thyroxine or continue Triiodothyronine (T3); however, if it is not covered by insurance the patient will be responsible.

If subjects discontinue study treatment prematurely for any reason they will be asked to continue follow-up until study completion.

All patients will be scheduled for a 12-month safety follow-up visit.

TABLE 1: SCHEDULE OF STUDY PROCEDURES

Study Phase	Screening	Study Visits			Follow Up Visit
Visit		3mo (+/- 14 days)	6mo (+/- 14 days)	9mo (+/- 14 days)	12mo (+/- 14 days)
ECOG PS	X	X	X	X	X
Informed Consent	X				
Review Inclusion/Exclusion Criteria	X				
Demographics/Medical History	X				
Physical Examination	X	X	X	X	X
Vital Signs: BP, HR, RR	X	X	X	X	X
EKG	X				
Disease assessment	X	X	X	X	X
FACT-B QOL questionnaire	X	X	X	X	X
Prior/Concomitant Medications	X	X	X	X	X
Clinical Laboratory Evaluation*	X	X	X	X	X
Pregnancy Test (women of childbearing potential only)	X				
Adverse Event Assessment	X	X	X	X	X

- *TSH, FreeT3, FreeT4, CBC, CMP every 4 weeks for the first 12 weeks and then every 12 weeks until end of study.
- Additional lab work at physician's discretion.

Study Drug

Cytomel (liothyronine sodium) is a commercially available compound which is a synthetic formulation of triiodothyronine. Study drug may be obtained from the Aultman Hospital Retail Pharmacy or the pharmacy of the participant's choice. The cost will be charged to the participant/insurance company unless they meet the hospital's indigent policy, in which case study drug will be provided free of charge.

Cytomel capsules should not be opened, crushed, or chewed. Patients should store the Cytomel capsules in the original package provided and be instructed to keep all medication out of reach of children. Further details obtained from accessdata.fda.gov can be found in appendix D.

HOW SUPPLIED

Cytomel (liothyronine sodium) Tablets: 5 mcg in bottles of 100;

25 mcg in bottles of 100; and 50 mcg in bottles of 100.

5 mcg 100's: NDC 52604-3414-1

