7.0 Statistical Methods

Baseline Data

Baseline and demographic characteristics will be summarized by standard descriptive summaries (e.g., means and standard deviations for continuous variables such as age and percentages for categorical variables such as gender).

Analysis of Primary Outcome of Interest

The primary analysis will include all subjects meeting all inclusion and exclusion criteria and completing Visit 1.

The primary endpoint will be the progression free survival at 12 months

Secondary endpoints will include:

- the prevalence of hypothyroidism in successive metastatic breast cancer patients,
- the change in QOL measures between baseline, 3, 6, 9 and 12 months and
- the duration of time to achieve the euthyroid hypothyroxiemic state

Sample Size and Power

The sample size is estimated to be approximately 30 patients.

Given the many uncertainties to calculate power precisely, this is an estimate made, based on clinical experience.

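### Progression is judged from examination, laboratory results and whatever routine imaging exists, with no named criterion, so the primary 12-month PFS can be overstated

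*Protocol*

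**What the plan says.** Protocol section 7.0 sets the endpoint: "The primary endpoint will be the progression free survival at 12 months". Section 3.0 gives the timing: "Disease status will be assessed at 3, 6, 9, and 12 months". The method stands in section 4.0, where disease state is judged "via clinical examination, laboratory results and radiographic findings performed as part of routine care".

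Nothing else in the protocol adds to that method:

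- Table 1 has a row for "Disease assessment" at screening and at every visit, with a window of 14 days either side for the month 3 to 12 visits, but no imaging row.
- The baseline work-up in section 3.0 is "All enrolled participants will undergo baseline screening lab work (TSH, FreeT3, FreeT4, CBC, CMP), EKG and physical examination". A baseline scan is not mentioned.
- The scheduled laboratory panel is "TSH, FreeT3, FreeT4, CBC, CMP every 4 weeks for the first 12 weeks and then every 12 weeks until end of study", with further tests at the physician's discretion.
- On care between visits, section 4.0 states: "Unscheduled visits and management for metastatic breast cancer are at the discretion of the investigator".
- Section 4.0 also states: "In the event of loco/regional recurrence or progression there is no need to discontinue study treatment because this is not one of the endpoints".

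**The concern.** The visits are scheduled but the scans are not. A month-12 visit with an examination and blood tests, and no imaging since month 9 or month 6, is compatible with the text. Such a patient can be recorded as progression-free although radiographic progression may have occurred after the last scan. Without a named criterion, the same findings could also be called progression in one patient and not in another.

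The whole primary result rests on this call. There is no concurrent arm with the same pattern of assessment, so the error does not cancel, and any comparison with an outside PFS rate takes all of it.

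**Working it through.** **Plan's own figure.** There is none to reproduce. Section 7.0 gives about 30 patients on clinical experience, with no reference PFS rate, target rate, alpha or power. The documents give no scan interval. The PFS medians, scan gaps and detection shares below are assumptions.

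**Model.** Let PFS be exponential with median M, so S(t) = 0.5^(t/M). Let every patient's last scan lie g months before month 12, and let d be the share of events in that gap found otherwise (examination, laboratory results, symptoms, death). Then

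observed 12-month PFS = S(12) + (1 − d) × [S(12 − g) − S(12)].

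| Median M (months) | True S(12) | g = 3, d = 0 | g = 3, d = 0.5 | g = 6, d = 0 | g = 6, d = 0.5 |
|---|---|---|---|---|---|
| 6 | 25.0% | 35.4% | 30.2% | 50.0% | 37.5% |
| 9 | 39.7% | 50.0% | 44.8% | 63.0% | 51.3% |
| 12 | 50.0% | 59.5% | 54.7% | 70.7% | 60.4% |
| 18 | 63.0% | 70.7% | 66.9% | 79.4% | 71.2% |

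Example for M = 9: S(12) = 0.5^(12/9) = 0.397, S(9) = 0.500 and S(6) = 0.5^(6/9) = 0.630. With g = 3 the excess is 0.500 − 0.397 = 0.103 at d = 0, or 3.1 of 30 patients, and half of that at d = 0.5. With g = 6 it is 0.630 − 0.397 = 0.233, or 7.0 of 30 patients, and again half at d = 0.5.

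Across the four medians the excess is:

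- g = 3: 7.7 to 10.4 points at d = 0, and 3.9 to 5.2 points at d = 0.5.
- g = 6: 16.4 to 25.0 points at d = 0, and 8.2 to 12.5 points at d = 0.5.

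If only a fraction of patients lack a month-12 scan, and lacking it is unrelated to progression, the excess shrinks in proportion.

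**Opposite direction.** Suppose true PFS is 40% and 10% of truly progression-free patients are called progressed on weak grounds. The observed rate is 0.40 × 0.90 = 36%. If 10% of progressors are missed as well, it is 0.36 + 0.60 × 0.10 = 42%. The net sign depends on local practice.

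**Scale.** The exact 95% confidence interval for 12 of 30 is 22.7% to 59.4%. The misclassification error is not part of that interval.

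**Why censoring at the last scan is not a remedy.** Take ten patients at risk after a month-9 scan. None is rescanned, and one progresses clinically at month 11. If the nine event-free patients are censored at month 9 while the clinical event counts, the risk set at month 11 is one and the Kaplan-Meier estimate falls to zero. The naive proportion still progression-free is 9 of 10. Such censoring is informative and biases PFS downward.

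**The case against.** The strongest objection is scope. Event dating, censoring and reporting commonly belong in the SAP, which is not shown, and the fix adds no scans. Section 5.0 names office and hospital records as data sources, so some scan dates could be recovered later. This narrows the point but does not remove it: the method of judging the primary endpoint is stated in the protocol, and it leaves both the criterion and the imaging open.

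Four stronger readings are tempting, and the documents do not support them:

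- *PFS is inflated.* It can be. Routine scanning may turn out to be frequent, and loosely based calls can push the other way.
- *Laboratory values alone can trigger a progression call.* The text joins the three sources with an and; it does not say that any one suffices. Nor does it rule this out. Table 1 lists disease assessment apart from physical examination and laboratory evaluation, which hints at something more than those two, but nothing says what.
- *The investigator who titrates the drug also makes the call, unblinded.* Section 3.0 gives titration to the investigator. No section names who determines progression, and section 5.0 allows referral from other oncologists.
- *The overstatement is 8-10 or 16-25 points.* Those figures need every patient to have the same scan gap and nothing, not even a death, to be detected within it. They are upper figures under the assumed medians and gaps.

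It also stands that this is a pilot with no stated threshold or test, so no stated decision can be shown to reverse.

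**Conclusion.** The point holds as a weakness in a stated assessment rule: the plan allows an unscanned patient to be scored progression-free at month 12 and gives no criterion for progression. The bias is possible and of uncertain net direction. Where missed progression dominates, the illustration gives about 4-10 points for a 3-month scan gap and 8-25 points for a 6-month gap. The lower ends have half of the later events detected otherwise and the upper ends none. These figures rest on exponential PFS, medians of 6 to 18 months and a common gap for all patients, none of which comes from the protocol.

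Section 4.0 also conflicts with section 7.0. One calls loco/regional recurrence or progression not an endpoint; the other makes PFS primary. A reader might limit the section 4.0 remark to loco/regional events, but the text does not say that such events fall outside PFS. The change is worth making before the primary result is reported.

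**What to change.** No scans need to be added.

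1. In section 4.0, define a PFS event as progression by RECIST 1.1 on routine-care scans, unequivocal clinical progression, or death. State that laboratory values alone are not progression.
2. Record on the case report form the date of each scan and the date and basis of each progression call. Date the event at the scan, examination or death that showed it.
3. Do not censor unscanned event-free patients at their last scan while still counting clinical events. Report 12-month PFS with bounds: count event-free patients without imaging in the month-12 window first as progression-free, then as progressed. With u such patients among 30, the bounds lie u/30 apart (3 patients give 10 points). Report the share of patients imaged in each window.
4. Reconcile the section 4.0 remark about progression and endpoints with the primary endpoint in section 7.0. This concerns the status of progression as an endpoint only; it takes no position on study treatment after progression.

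The cost is protocol and case report form wording, applying the criteria to scans already done, and slightly more analysis. The reported range will be wider and less favourable than a single figure.

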Cross sectional retrospective compassionate use study inducing euthyroid hypothyroxinemia successfully reported improved progression free and overall survival in patients with high grade synovial sarcoma and brain stem glioma 8 and 7 years. (2,3)

Rationale and Hypothesis

The rationale of this study is to replace L-thyroxine (T4) with Triiodothyronine (T3) in hypothyroid patients with metastatic breast carcinoma while they continue to receive standard systemic therapy, titrating the dose to achieve a state of euthyroid hypothyroxinemia which in turn would result in a lower risk of disease progression and improved survival by lowering the concentration of T4.

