2.0 Primary Objective

1. To prospectively evaluate the progression-free survival in hypothyroid patients with metastatic breast carcinoma who are rendered euthyroid and hypothyroxinemic.

Secondary Objectives

1. To quantitate the prevalence of hypothyroidism in metastatic breast cancer patients.
2. To monitor QOL at baseline, 3, 6, 9 and 12 months.
3. To prospectively study the feasibility and average time required to achieve the euthyroid hypothyroxinemia state in qualifying patients.

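### Is progression-free survival at 12 months the wrong endpoint when protocol T3 stops at 9 months and thyroxine may then be resumed?

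*Protocol*

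**What the plan says.** - **Objective (Protocol, 2.0):** "To prospectively evaluate the progression-free survival in hypothyroid patients with metastatic breast carcinoma who are rendered euthyroid and hypothyroxinemic". No time point is attached.
- **Hypothesis (Protocol, 1.0, Rationale and Hypothesis):** replacing T4 with T3 is expected to bring "a lower risk of disease progression and improved survival by lowering the concentration of T4".
- **Treatment and assessment (Protocol, 3.0):** "Treatment duration will be 9 months. Disease status will be assessed at 3, 6, 9, and 12 months". Section 4.0 gives the same duration as 270 days and adds: "Day 1, or day 5 (if washout required) will be the day of the first dose of Triiodothyronine treatment".
- **After treatment (Protocol, 4.0, Discontinuation of Study Treatment):** "At the end of the treatment period, the investigator will have the discretion to resume thyroxine or continue Triiodothyronine (T3"). Patients who stop early are asked to stay in follow-up, and "All patients will be scheduled for a 12-month safety follow-up visit".
- **Endpoint (Protocol, 7.0):** "The primary endpoint will be the progression free survival at 12 months". The secondary endpoints are prevalence, quality of life and time to the target state. PFS at another time is not listed.
- **Population:** section 3.0 names an intent-to-treat population. Section 7.0 includes eligible patients who complete Visit 1. Neither depends on the thyroid therapy given after month 9.

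**The concern.** The hypothesis credits benefit to a low T4 level, yet the only PFS figure named is read three months after the protocol stops controlling T4. In those months some patients may be back on thyroxine, the agent the study set out to remove, and others still on T3. The choice is the investigator's, and section 4.0 makes the patient responsible for continued T3 that insurance does not cover.

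If the effect fades when thyroxine returns, the 12-month figure would understate what T3 did while it was given. Read alone, it also would not separate progression during protocol treatment from progression afterwards. Disease is already assessed at month 9, so leaving a 9-month figure off the endpoint list looks like an oversight, and one that might allow a favourable time point to be chosen later.

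**Working it through.** **1. Do the sections contradict each other?** Side by side they give one sequence: 9 months of T3, thyroid therapy at discretion, a visit for everyone at month 12 with a disease assessment in Table 1, and PFS at 12 months. The objective fixes the patients and the outcome but no time. The summary of changes for version 4.0 shows that the 12-month wording was set deliberately. There is nothing to reconcile.

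**2. How much of the window is off protocol treatment?** The first dose is on day 1 or day 5, followed by 270 days of treatment.
- Shortest: 360 − 274 = 86 days; 86/360 = 23.9%.
- Longest: 365 − 270 = 95 days; 95/365 = 26.0%.
- The ±14 days allowed for the 12-month visit widen this to 86 − 14 = 72 and 95 + 14 = 109 days.

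The gap is real.

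**3. What could it do to the estimate?** The Protocol gives no reference rate, effect size or resumption share, so all three are assumed. Let p be 12-month PFS without effect (30 to 50%), HR the on-treatment hazard ratio (0.5 to 0.7), and f the share of patients progression-free at month 9 who resume thyroxine and lose the effect at once. Hazards are constant within each period.

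- 9-month PFS: S9 = p^(0.75·HR), against p^0.75 without effect.
- 12-month PFS: S12 = S9·[f·p^0.25 + (1 − f)·p^(0.25·HR)], against p.

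For p = 0.4 and HR = 0.6, S9 = 0.4^0.45 = 66.2%, against 0.4^0.75 = 50.3%: a gain of 15.9 points at 9 months. At 12 months:

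| Resume thyroxine | PFS at 12 months | Gain over 40% | Compared with the 9-month gain of 15.9 |
|---|---|---|---|
| None (f = 0) | 57.7% | 17.7 points | larger |
| Half (f = 0.5) | 55.2% | 15.2 points | within 1 point |
| All (f = 1) | 52.7% | 12.7 points | about 3 points smaller |

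Across the nine combinations of p (0.3, 0.4, 0.5) and HR (0.5, 0.6, 0.7):
- **None resume:** the 12-month gain exceeds the 9-month gain by 0.4 to 3.1 points.
- **Half resume:** it lies between 0.1 points above and 2.2 points below.
- **All resume:** it is 1.6 to 6.0 points below. The loss relative to a sustained effect is 27 to 31% of the gain (3.1 to 7.7 points).

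**4. Could this trial see it?** The 95% half-width at n = 30 near 50% is 1.96·√(0.25/30) = 17.9 points. Even the worst case is well inside that. Events expected in months 9 to 12 are 30·(S9 − S12), which is 1.9 to 5.0.

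**5. Would PFS at 9 months isolate the hypothyroxinemic state?** No.
- It still counts the time before the state is reached, which is itself a secondary endpoint.
- It still counts patients who stop T3 early and stay in follow-up.
- Section 4.0 takes imaging from routine care, so progression that begins on T3 may be detected only after month 9.
- The month-9 visit has a ±14 day window and may fall before or after the end of treatment.

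Both figures describe the strategy as started. They differ in when it is read.

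**The case for a change.** The strongest argument for the concern is one of interpretation. Therapy in months 9 to 12 is neither fixed nor random. In a single-arm study of about 30 patients, it helps to know which exposure a PFS figure describes. A 9-month estimate needs no extra visit, test or patient, and naming it in advance would stop anyone choosing between time points later. A descriptive table of month 9 to 12 events by thyroid therapy could sit beside it.

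Part of this stands. A report of 12-month PFS should say that it reflects 9 months of T3 followed by discretionary therapy, and a supportive 9-month estimate would be sensible. But an extra time point on the same curve is what a protocol commonly leaves to the statistical analysis plan, and whether that plan has it cannot be checked here. The primary time point is already fixed, so the primary result is not open to later choice. The proposed table would split about 2 to 5 events by a therapy chosen at discretion and possibly influenced by cost. It would be confounded and nearly empty.

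The laboratory wording adds nothing. The sentence in section 4.0 that ends testing when study drug stops is limited to the treatment period, while the Table 1 footnote covers the whole study.

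**Conclusion.** The concern does not hold. The observation is correct: 24 to 26% of the 12-month window lies after protocol T3, and T4 may be restored in that time. Even so, the Protocol states nothing wrong and does not contradict itself, and PFS at 12 months is a legitimate endpoint for the strategy it describes. Under the assumed rates, the 12-month gain runs from about 3 points above the 9-month gain (none resume) to 6 points below it (all resume, effect lost at once), against a half-width of about 18 points. These sizes rest on the assumed PFS rates, hazard ratios and resumption shares, on constant hazards within each period, and on immediate loss of effect. The conclusion that there is no error does not depend on them. It follows from an objective without a time point, follow-up of all patients to month 12, and an endpoint fixed at that visit. A 9-month estimate is a matter of preference for the analysis plan and would not change the primary result.
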